
3 Design and Procedures

3.1

Evaluate the efficacy of the intervention for increasing vaccine uptake among adolescents and identify barriers and facilitators affecting the implementation of the school-based intervention in rural North and South Carolina.

Primary hypothesis: The proportion of age-eligible adolescents in intervention schools who receive at least one dose of the HPV vaccination will increase post-intervention implementation when compared with proportion prior to intervention implementation

Secondary hypothesis: Compared to the proportion of age-eligible adolescents who receive at least one dose of the HPV vaccine in control counties, we will see an increase in the proportion of age-eligible adolescents who receive at least one dose of the HPV vaccine in intervention counties after intervention implementation.

Procedures:

(a) Caregiver Survey: Caregivers (parents and legal guardians) of 6th, 7th, and 8th graders from schools in the intervention counties will be invited to opt-in to surveys where we will collect quantitative data to explain intervention implementation, reach, and effects. All caregivers of 6th-8th graders in the intervention schools will be eligible to participate in the survey, and response rates up to 1000/county (n=2000 total) are possible. The survey will be conducted pre-implementation of the intervention and collect caregiver and adolescent demographics, HPV vaccine knowledge, attitudes towards vaccination, access to healthcare, intervention exposure and caregiver-reported adolescent vaccine uptake. Surveys will be self-administered remotely, or by the study team in person or over the phone. All surveys will be completed electronically although paper-versions may be used if access to electronic systems are limited at the time of the survey. Any data from paper-surveys will be entered by study staff using the electronic survey system.

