(e) Post-training evaluation surveys: Professional development or training sessions may consist of courses provided by Duke, other organizations or created by the study team members. If the course is created by study staff members, these materials will be submitted to the IRB in a future amendment. This course could contain material regarding misinformation, motivational interviewing, vaccine registry information and other information determined to be useful by study team members. School nurses, local healthcare providers, and other individuals who take part in any professional development and/or training sessions as part of the intervention will be asked to provide feedback on the training using structured evaluation forms. Evaluation questions will include prompts to elicit feedback on the knowledge gained, residual information gaps, training format and duration, and suggestions for improvements. Closed (e.g., rating scales) and open ended questions on these topics will be included in the survey and tailored to the content covered in the training. As much as possible, data will be collected via electronic surveys, and time will be provided at the end of the training session for completion of the evaluation surveys. Study staff may follow up and complete surveys on the phone or in-person with individuals who are unable to access the surveys for any reason. The surveys will be available in English and take approximately 5 min to complete.

(f) Fidelity Checklists: School nurses in the intervention schools will be asked to complete brief fidelity checklists to document intervention implementation at regular intervals during the study period. Due to the nature of the checklists, only those nurses who are directly involved in intervention implementation will be included in this activity. The checklists may be completed by the nurses on paper or using a link to an electronic survey. Study staff may administer the checklist over the phone and enter data into the electronic survey. In general, the administration of the checklist will occur after each intervention activity (e.g., after each newsletter is due for dissemination). Regular implementation meetings will be held by the study team to offer technical support to school nurses.

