Caregiver Survey: Eligible caregivers will be able to opt in to the surveys by using QR codes or links that will be listed on the bottom of the health newsletters (letters will be submitted in future amendment). The link to the survey will also be sent out through emails and social media blasts. To ensure that we reach caregivers without technology access, we will also use flyers and mailings to reach eligible caregivers. Information about the study may also be distributed or communicated in person at venues such as football games, orientation sessions, PTA meetings or related activities where eligible caregivers or their adolescents may be present.

Caregiver Interview/Focus Group: We will employ a combination of school-, community-, social media- and web-based strategies to seek participants. Eligible participants include caregivers who have a middle schooler in County 2, NC or County 1, SC. Participants will be recruited through one or more of the following methods: letters, emails, newsletters and social media. A url and/or QR Code to an interest/enrollment survey will be provided as well as a phone number for those who are interested in the study but do not have access to the internet or prefer to communicate by phone.

Local Stakeholder Interview/Nurse surveys: Nurses, health providers, and stakeholders will be recruited based on existing networks of the study team, via email, phone, or mailings. In addition to this purposive strategy, we will use snowball sampling, based on recommendations of current or prospective participants, to reach other relevant participants.

Post-Training Evaluation Survey, Fidelity Checklist, Vaccine Outcome Assessment: School nurses will be providing the vaccination outcome data and feedback regarding the intervention in the form of the post-training evaluation survey, fidelity checklist and focus groups.

6 Risk/Benefit Assessment

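### The caregiver survey is labelled pre-implementation, yet one route into it is a link on what appear to be the intervention newsletters, and the analysis does not separate those respondents

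*Combined protocol and SAP*

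**What the plan says.** All references are to the combined protocol and SAP.

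- **Timing, Section 3.1(a).** "The survey will be conducted pre-implementation of the intervention". No other caregiver survey wave is described.
- **Purpose and content, Section 3.1(a).** The survey is to "collect quantitative data to explain intervention implementation, reach, and effects". Besides demographics, knowledge, attitudes and access to care, it records "intervention exposure and caregiver-reported adolescent vaccine uptake".
- **Recruitment, Section 5.** Eligible caregivers opt in "by using QR codes or links that will be listed on the bottom of the health newsletters". The newsletters themselves are left to a later amendment. Other routes follow: "The link to the survey will also be sent out through emails and social media blasts"; "we will also use flyers and mailings to reach eligible caregivers"; and "Information about the study may also be distributed or communicated in person at venues such as football games".
- **Status of newsletters, Section 3.1(f).** Nurses complete the fidelity checklist "after each intervention activity (e.g., after each newsletter is due for dissemination".
- **Analysis, Section 7.** The survey's dependent variable is coverage with at least one HPV dose. The listed correlates include parental attitudes, access to primary care and barriers. Neither recruitment route nor reported exposure is listed as a covariate, stratum or exclusion.
- **Vaccination outcome, Section 3.1(g).** This comes from school-district data sets, not from the survey.

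**The concern.** A caregiver who follows a link at the foot of a newsletter has that newsletter in hand before answering any question. If the newsletter is part of the intervention, the answers on knowledge, attitudes and barriers were given after exposure but are filed as pre-implementation.

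Two survey results are at stake. The first is the description of knowledge, attitudes and barriers before the intervention, which would mix exposed and unexposed caregivers in unknown proportions. The second is the set of regression associations between attitudes or barriers and uptake. A newsletter could change a stated attitude on the day, while the child's vaccination status reflects decisions already taken, so for these respondents the two sides of the model would refer to different times.

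Only one wave is described, so no later caregiver survey would reveal the problem. If responses are stored without a route marker, the route cannot be recovered afterwards.

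**Working it through.** **Step 1. Set the sections side by side.**

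| Section | What it implies for the survey |
|---|---|
| 3.1(a), timing | Fielded before implementation |
| 3.1(a), content and purpose | Measures exposure, reach and effects, so some respondents must already be exposed |
| 5 | Newsletter link is one of several routes in |
| 3.1(f) | Sending a newsletter is an intervention activity |
| 7 | All responses analysed together |

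There are two conflicts. One lies inside Section 3.1(a): a survey completed wholly before implementation has no exposure or reach to measure. The other lies between Sections 3.1(a), 5 and 3.1(f): a respondent recruited from an intervention newsletter is not a pre-implementation respondent.

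**Step 2. Is it the same newsletter?** The documents do not say so. They describe no second newsletter, however. Section 1 makes education of parents by school nurses the core component, and Section 4(b) treats having seen nurse-supplied health education materials as one way to qualify for the post-intervention caregiver interviews. Identity is a strong inference, not a stated fact.

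**Step 3. Reproduce the plan's own figure.** Section 3.1(a) gives a ceiling of 1000 responses per county: 2 × 1000 = 2000, as stated. This is a maximum, not a powered sample size. No alpha, power or effect size is given for the survey.

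**Step 4. Possible size, by assumption only.** Let f be the share of respondents entering by newsletter, and d the difference in percentage points between their answers and those of the others. That difference combines any effect of reading the newsletter with any difference in who reads it. The shift in a pooled percentage is f × d. The documents give neither input.

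| f | d = 2 | d = 5 | d = 10 |
|---|---|---|---|
| 0 | 0 | 0 | 0 |
| 0.25 | 0.5 | 1.25 | 2.5 |
| 0.50 | 1.0 | 2.5 | 5.0 |
| 0.75 | 1.5 | 3.75 | 7.5 |
| 1 | 2 | 5 | 10 |

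**Step 5. Scale.** Take the full 2000 responses, a proportion of 60% (the national one-dose HPV figure in Section 2.2, borrowed only for scale) and no clustering. The 95% half-width is 1.96 × √(0.6 × 0.4 / 2000) = 0.02147, or about 2.1 points. The shift exceeds this when d is larger than 2.147 / f: 8.6 points at f = 0.25, 4.3 at f = 0.50 and 2.9 at f = 0.75. Fewer responses or clustering within schools would widen the interval and raise these thresholds. The shift could thus be negligible or could exceed sampling error.

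**The case against.** Four points can be made for the plan.

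*The newsletter is only one route.* This stands. Emails, social media, flyers, mailings and in-person contact can reach caregivers who have seen no newsletter. A reader might infer that the whole survey is taken after first exposure. Section 5 does not support that: post-exposure timing follows only for newsletter entrants and for anyone answering after the first newsletter has gone out. Being listed first does not make the newsletter the main route.

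*The newsletters are unseen.* This stands in part. A first newsletter carrying little beyond the invitation would largely reconcile the sections. The plan does not say that one is intended, and a sentence would settle it.

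*The survey already records exposure, so exposed respondents can be identified.* This stands in part. A self-reported item could separate some of them, but Section 7 does not use it. The item also suggests that the pre-implementation label, rather than the newsletter link, may be the mistake. Simply dropping the link and closing the survey before the first newsletter would therefore leave exposure, reach and effects unmeasurable in the only wave described.

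*No before-after survey comparison is planned.* This stands. The plan does not call the survey a baseline, and a reader who infers a biased survey contrast would be assuming a second wave that is not described. The cross-sectional summaries and models in Section 7 remain exposed to the problem.

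**Conclusion.** The timing conflict is real and should be resolved before the survey is fielded or, if data are already in hand, before they are analysed. It concerns one recruitment route, and it rests on the inference that the health newsletters of Section 5 are the intervention newsletters of Section 3.1(f).

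The size cannot be derived from the documents. Under the assumed inputs it runs from zero (no newsletter entrants) to 7.5 points (three quarters of respondents and a 10-point difference), or the full 10 points if everyone entered that way.

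Two further readings go beyond the text. One is that knowledge is overstated and barriers understated: this is plausible, but the documents support no direction, and newsletter readers may differ from other caregivers before reading anything. Knowledge is also not among the correlates listed in Section 7, so for knowledge the concern is with the summaries rather than a planned model. The other is that the primary hypothesis is compromised: the vaccination outcome comes from school-district records under Section 3.1(g) and is not directly affected.

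**What to change.** 1. Reconcile Sections 3.1(a), 3.1(f) and 5. State the opening and closing dates of the survey relative to the first newsletter in each district, and say whether the newsletter carrying the link is an intervention newsletter.
2. In Section 5, give each recruitment route its own link or URL, and add a route field for surveys done on paper, by phone or in person.
3. In Section 7, label a response as post-exposure if it came through a newsletter, reports exposure, or is dated after the first newsletter in that district.
4. Exclude post-exposure responses from the pre-implementation summaries and regression models, and use them only for the exposure and reach questions. Report the number of responses by route and by exposure label.

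This keeps the newsletter route and the exposure item, so the purpose stated in Section 3.1(a) is still served. The cost is a wording change in these sections, several survey links instead of one, and fewer responses in the pre-implementation analyses. Those analyses will still rest on an opt-in sample; the change deals with exposure, not with self-selection.
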